11.7 Changes in the Conduct of the Study or Planned Analysis

Any changes to the conduct or planned analyses will be handled via protocol or SAP amendment, respectively.

12 Regulatory, Ethical, and Legal Obligations

12.1 Declaration of Helsinki

The investigator will ensure that this study is conducted in accordance with the most recent revision of the Declaration of Helsinki.

12.2 Good Clinical Practice

The study will be conducted according to the study protocol and to Standard Operating Procedures that meet ICH GCP guidelines for clinical studies.

12.3 Research Ethics Board

Before implementing this study, the protocol, the proposed subject ICFs, and other information for the subjects must be reviewed by a properly constituted committee or committees responsible for approving clinical studies. The REB-written and -signed approval letter/form must contain approval of the designated investigator, the protocol (identifying protocol title, date, and version number), and of the subject ICF (date, version).

12.4 Regulatory Authority Approval

The study is utilizing all products as per their licensed usage and indications. No regulatory approval will be required.

12.5 Informed Consent

Written informed consent is to be obtained from the subject prior to enrollment into the study.

All subjects will be required to participate in the consent process. During the consent process, the person obtaining consent will inform the subject of all elements of informed consent. No protocol-specific procedures, including screening procedures will be performed until the subject has signed and dated an REB-approved ICF. Study participation will start with the signing and dating of the ICF.

The investigator must ensure that the subject is given full and adequate oral and written information about the nature, purpose, and possible risk and benefit of the clinical trial. Subjects must also be notified that they are free to withdraw from the clinical trial at any time without prejudice to future care. The subject should be given the opportunity to ask questions and allowed time to consider the information provided.

In case of a clinical trial protocol amendment, the subject information sheet and ICF need to be revised to reflect the changes, if needed. Also, if the subject information sheet and ICF are revised, they must be reviewed and approved by the responsible REB, and signed by all subjects subsequently enrolled in the clinical trial as well as those currently enrolled in the clinical trial.

12.6 Subject Confidentiality and Disclosure

A report of the results of this study may be published or sent to the appropriate health authorities in any country in which the study drug may ultimately be marketed, but the subject's name will not be disclosed in these documents. The subject's name may be disclosed to the sponsor, Allergan, or the governing health authorities including Health Canada if they inspect the study records. Appropriate precautions will be taken to maintain confidentiality of medical records and personal information.

In accordance with Canadian privacy requirements, additional purposes of this study include the following: to publish anonymous subject data from the study, and to create and maintain a data repository.

12.7 Sponsor Monitoring of Study Documentation

A representative of Allergan will monitor the study on a periodic basis. The determination of the extent and nature of monitoring will be based on considerations such as the objective, purpose, design, complexity, blinding, size, and endpoints of the study. This will be detailed in the study monitoring plan.

Authorized representatives of Allergan or regulatory authority representatives will conduct on-site visits to review, audit and copy study-related documents. These representatives will meet with the investigator(s) and appropriate staff at mutually convenient times to discuss study-related data and questions.

12.8 Study Documents

The investigator must maintain source documents for each subject in the study, including all demographic and medical information etc., and keep a copy of the signed and dated ICF. All information on the eCRFs must be traceable to these source documents in the subject's file. Data without a written or electronic record will be defined before study start and will be recorded directly on the eCRFs which will be documented as being the source data.

12.9 Collection of Study Data

This study will be conducted in compliance with Health Canada requirements. The investigator is responsible for ensuring that study data are properly recorded on each subject's eCRFs and related documents. An investigator who has signed the protocol signature page should personally sign for the eCRFs (as indicated in the eCRFs) to ensure that the observations and findings are recorded on the eCRFs correctly and completely. The eCRFs are to be submitted to Allergan in a timely manner at the completion of the study, or as otherwise specified by Allergan.

The data reported on the eCRFs shall be derived from source documents and be consistent with these source documents, and any discrepancies shall be explained in writing. Any change or correction to data reported on an eCRF shall be dated, initialed and explained, if necessary, and shall not obscure the original entry (ie, an audit trail shall be maintained); this applies to both written and electronic changes and corrections.

12.10 Disclosure of Information

This study will be registered and results posted on www.ClinicalTrials.gov. Allergan, as the sponsor, has proprietary interest in this study. Authorship and manuscript composition will reflect joint cooperation between study investigators and Allergan personnel. Authorship will be established prior to the writing of the manuscript. As this study involves multiple centers, no individual publications will be allowed prior to completion of the final report of the multicenter study except as agreed with Allergan.

12.11 Discontinuation of the Study

It is agreed that, for reasonable cause, either the investigator or Allergan may terminate the investigator's participation in this study after submission of a written notice. Allergan may terminate the study at any time upon immediate notice for any reason, including the Allergan's belief that discontinuation of the study is necessary for the safety of subjects.

3 LIST OF ABBREVIATIONS

Abbreviation	Definition
AE	adverse event
BMI	body mass index
CFLs	crow's feet lines (also known as lateral canthal lines in BOTOX product literature)
DCA	deoxycholic acid
eCRF	electronic case report form
EOS	End of Study
FACE-Q	A clinically useful, patient-reported outcome measure (PROM) of satisfaction and quality of life following elective surgical and nonsurgical facial rejuvenation.
FWS	facial wrinkle scale
GAIS	global aesthetic improvement scale
GLs	glabellar lines
ICF	informed consent form
ISR	injection site reaction
PAAQ	periorbital aesthetic appearance questionnaire
SAE	serious adverse event
SAP	statistical analysis plan
SMF	submental fat
SMFRS	submental fat rating scale
SOPS	SkinMedica overall photodamage scale
SPA	self-perception of age
SSRS	subject self-rating scale
USADE	unanticipated serious adverse device effect

[figure not shown]
4 INTRODUCTION

The objective of the initial USA HARMONY study was to observe the safety and overall aesthetic impact of treating subjects with several modalities in an attempt to achieve subjects' desired clinical outcome. The Canada Global HARMONY study will expand upon the products tested, the facial areas treated, and the quantification of the psychological and emotional impact of the comprehensive aesthetic treatment provided and will ultimately be global in scope.

In the Global HARMONY study, subjects will be evaluated by the investigator to receive BOTOX Cosmetic, BELKYRA, Juvéderm facial fillers (JUVÉDERM VOLITE, JUVÉDERM VOLBELLA with Lidocaine, JUVÉDERM VOLIFT with Lidocaine, and JUVÉDERM VOLUMA with Lidocaine), and SkinMedica products. Selected subjects will receive staged treatment with the multiple products and will be evaluated using validated patient-reported outcome measurements to determine the psychological and emotional impact of an integrated treatment approach to reduce visible signs of aging.

The clinical hypothesis of this study is that subjects treated with a combination of BOTOX Cosmetic, BELKYRA, JUVÉDERM facial fillers, and SkinMedica products will have a significantly higher satisfaction with their overall facial appearance at the final study visit when compared with baseline, pre-treatment satisfaction scores, as measured by the mean change from baseline on the FACE-Q Satisfaction with Facial Appearance Overall Scale.

Overall Study Design

All subjects will sign an informed consent form (ICF), and begin the study at the screening visit (V0). Subjects receiving BELKYRA treatment will enter the study at V1 continuing on through V12. There will be no less than 1 month between repeat BELKYRA treatments and the final BELKYRA treatment. Subjects not receiving BELKYRA following screening (V0) will enter the

study at V7 to begin treatment with fillers, SkinMedica, and BOTOX Cosmetic as indicated in the study design diagram above.

All adverse events (AEs) including injection site reactions (ISRs) will be collected from when the ICF is signed through to the last study visit. Serious adverse events (SAEs) will be reported directly to Allergan and SkinMedica within 24 hours.

5 OBJECTIVES

5.1 Primary Objective

The primary objective of this study is to quantify the psychological, social and emotional impact of comprehensive aesthetic treatment with a portfolio of Allergan products by measuring the change in subject's satisfaction with facial appearance from baseline (before any treatment) to the final study visit (FACE-Q™: Satisfaction with Facial Appearance). These Allergan products include BOTOX® Cosmetic, BELKYRA®, Juvéderm HA facial fillers, and SkinMedica® topical nonprescription skin care products, as described in Section 9.

5.2 Secondary Objectives

Secondary objectives are:

- To determine the subject's self-appraisal of expectations of life change (FACE-Q™: Expectations), age-related facial appearance (FACE-Q™: Aging Appraisal), psychological function (FACE-Q™: Psychological Function), social function (FACE-Q™: Social Function) and overall satisfaction with skin (FACE-Q™: Satisfaction with Skin Questionnaire).
- To quantify the investigator's and subject's assessment of aesthetic improvement.

6 PATIENT POPULATIONS

6.1 Full Analysis Populations

Full analysis population is defined as all subjects who have met all eligibility criteria at the screening visit (V0) and received any product used as treatment in this study.

6.2 Evaluable Population

Evaluable population is defined as all subjects as defined in the Full Analysis Population who have had at least one post-treatment efficacy assessment at the final visit (V12).

The Full Analysis Population will be used for subject disposition, demographics and baseline characteristics summary will be used for safety analyses. The Evaluable Population will be used on demographics and key efficacy endpoints as well.

6.3 Subgroups

Two subgroups will be examined separately:

1. Gender: As male and female subjects may have differing expectations/perceptions of aesthetic improvement, they will be examined separately.
2. BELKYRA: As it is expected that approximately two-thirds of the enrolled population will not be treated with BELKYRA, subjects treated and not treated with BELKYRA will be examined separately.

7 SUBJECT DISPOSITION

The number and percentage of subjects of the Full Analysis Population will be summarized by treatment group and overall. The number and percentage of patients for the following categories will be displayed:

- Enrolled
- Treated
 - BELKYRA
 - Non-BELKYRA
- Completed the Study
 - Yes
 - No
- Primary Reason for Discontinuation:
 - Adverse Event
 - Termination by Investigator/Sponsor
 - Lost to Follow-Up
 - Personal Reasons
 - Protocol Violation
 - Other

Screen-failure patients (i.e., patients screened but not treated) and the associated reasons for failure to enroll will be tabulated overall for the all screened patients. The number and percentage of patients who complete the V12 and of patients who prematurely discontinue during the same period will be presented for each treatment group and pooled across treatment groups for the Full Analysis Population. The reasons for premature discontinuation from the V12 as recorded on the termination pages of the electronic case report forms will be summarized (number and percentage) by treatment group for the Full Analysis Population. All patients who prematurely discontinue during the V12 will be listed by discontinuation reason for the Full Analysis Population.

8 DEMOGRAPHICS AND OTHER BASELINE CHARACTERISTICS

8.1 Demographics

Age, Fitzpatrick skin type, height, weight, BMI at baseline will be summarized descriptively with Full Analysis population. Women of childbearing potential comprises women who have experienced menarche and who have not undergone successful surgical sterilization (hysterectomy, bilateral salpingectomy, or bilateral oophorectomy) or who are not post-menopausal. Number and percentage of female subjects of childbearing potential and in pregnancy are reported.

The demographic information will be listed.

8.2 Baseline characteristics

All FACE-Qs, SPA, PAAQ will be reported.

8.3 Medical History

A summary of medical history will be presented by system organ class (SOC) and preferred term (PT) using Medical Dictionary for Regulatory Affairs® (MedDRA) Version 21.0 or higher.

In addition, medical and surgical history will be listed.

8.4 Concomitant Medications

Therapy considered necessary for the subject's welfare may be given at the discretion of the investigator, including but not limited to medications for other conditions (i.e., hypertension, diabetes, etc.), treatment of AEs, estrogens, androgens, anti-androgenic agents, vitamins, iron supplements, folate, and herbal supplements. Medications should be taken consistently throughout the study and at the investigator's discretion.

Concomitant medications encompass all medicinal products that the subject was taking prior to the day 0 visit that are ongoing at the visit, in addition to all medications that have a start date on or after the day 0 visit date.

Concomitant medications will be summarized descriptively using frequency tables by ATC class and preferred name by treatment group and overall.

In addition, individual listing will be generated for all medication.

8.5 Clinical Scales for Treatment Inclusion Only

FWS, SMFRS and other inclusion/exclusion criteria will not be reported.

9 EXTENT OF EXPOSURE AND TREATMENT COMPLIANCE

Subject study product exposure and compliance will be summarized using descriptive statistics for each product, combination of multiple products, and overall exposure respectively during the treatment period.

10 EFFICACY ANALYSES

The primary efficacy endpoint is the change from baseline to the final visit in the overall Rasch-transformed scores of the FACE-Q™ Satisfaction with Facial Appearance Scale. The scale data will be analyzed by using paired t-test. If normality is unmet, Wilcoxon signed-rank test is used to replace paired t-test. If skewness of FACE-Q change from baseline is not close to zero, the change data of FACE-Q is not considered as normally distributed. In this case, one-way nonparametric procedure with Wilcoxon option will be used to replace paired t-test.

One-sample paired t-test is performed on changes at end of study. The following statistics will be provided;

Label of Statistics	Description
N	Number of subjects of overall or a subgroup
Mean	Mean change of FACE-Q™ Scale
SD	Standard deviation of Mean Change
SEM	Standard error of Mean Change
Median	Median of Changes
Minimum, Maximum	Minimum, Maximum (of Changes)
Pr > t	p value of Mean Change through paired t-test, or that of Wilcoxon signed-rank test
95% CIs	95% Confidence Intervals of the Mean, lower and upper limits

The efficacy analyses will be based on the Evaluable population. Baseline for efficacy is defined as the last nonmissing assessment before the first dose of study treatment. All statistical tests will be 2-sided hypothesis tests performed at the 5% level of significance for main effects. All confidence intervals will be 2-sided 95% confidence intervals, unless stated otherwise.

Hypothesis testing will be performed at a 0.05 significance level (2-sided). Since BELKYRA and without BELKYRA are the major treatment cohorts, unless specified, all endpoints will be summarized by those two groups (BELKYRA and without BELKYRA) and overall respectively. However, this study is not designed to compare the efficacy and safety outcomes between subjects treated with BELKYRA and those treated without BELKYRA. All discussion and interpretation related to study outcomes will be mainly focused on the overall results.

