10.2 Primary Efficacy Parameter

The primary endpoint is the change from baseline in the Rasch-transformed score of the FACE-Q™ Satisfaction with Facial Appearance Overall Scale to the final study visit.

The primary efficacy parameter will be summarized by treatment group and overall, as well as by subgroup being defined in Section 6.3 Subgroup. Two treatment groups are defined as BELKYRA and without-BELKYRA. Overall efficacy is summarized by both groups.

Subgroups of gender and treatment are treated as separate cohorts. There is no between groups analysis to be performed.

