10.3 Secondary Efficacy Parameters

The same analysis procedures and methods used for the primary efficacy endpoint will be applied for the secondary efficacy endpoints, which include FACE-Q Expectations, FACE-Q Aging Appraisal, FACE-Q Psychological Function Scale, FACE-Q Social Function scale and FACE-Q Satisfaction with Skin.

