10.3.2 Other Efficacy Endpoints

In general, summaries are provided in frequency and percentage for both of assessments by investigators and subjects, and by subgroups at V12. No statistical testing will be performed for other efficacy endpoints.

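### SAP section 10 names two different replacements for the primary paired t-test under one condition, and the second does not test within-subject change

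*SAP*

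**What the plan says.** SAP section 10 starts from a paired t-test and adds: "If normality is unmet, Wilcoxon signed-rank test is used to replace paired t-test". It then says what counts as non-normal. The trigger is "If skewness of FACE-Q change from baseline is not close to zero", with no number, and data meeting it are to be treated as not normal. The next sentence gives the consequence: "In this case, one-way nonparametric procedure with Wilcoxon option will be used to replace paired t-test".

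Elsewhere the plan points one way:

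- SAP section 10 states: "One-sample paired t-test is performed on changes at end of study".
- The p-value row of its output table reads: "p value of Mean Change through paired t-test, or that of Wilcoxon signed-rank test".
- The Protocol synopsis (Primary Efficacy Analysis) and Protocol 11.4.1 name the paired t-test, with signed-rank as the only alternative.
- SAP section 18 declares no departure from the protocol's analyses.
- SAP 10.2 says of the gender and BELKYRA cohorts: "There is no between groups analysis to be performed".

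The rule reaches beyond the primary endpoint. SAP 10.3 says: "The same analysis procedures and methods used for the primary efficacy endpoint will be applied for the secondary efficacy endpoints", and lists five further FACE-Q scales. For PAAQ the SAP disagrees with itself. Section 10.3.2 says "No statistical testing will be performed for other efficacy endpoints", while 10.3.2.2, which sits under it, has the transformed PAAQ scores handled like the primary endpoint.

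**The concern.** The skewness sentence defines the condition that the signed-rank sentence relies on. The SAP therefore gives two differently named procedures for the same event.

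The two are not interchangeable. Signed-rank works on one column of within-subject changes and asks whether they centre on zero. A one-way Wilcoxon procedure, as the term is normally used, ranks observations across two or more independent groups and asks whether the groups differ. The primary endpoint is a single column of changes with no second group.

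At stake is the primary p-value and, through SAP 10.3, the p-values of five secondary scales. A programmer who follows the last and most operational sentence would have to supply a grouping that the SAP never gives, and could produce a p-value for a different question or one that ignores the pairing.

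**Working it through.** **1. Is the second procedure a new test or another name for the first?** The trigger is the same (non-normal changes), and so is the role (replacing the paired t-test). The name is different, and no grouping variable is given. SAP section 15, which would identify the software, is redacted. That is not a fault in the plan, but it means the visible text cannot show which routine was meant.

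**2. Inputs.** From SAP section 14 and Protocol 11.6: 48 evaluable subjects, mean change 12.0, SD 20.0, two-sided 5% level, 20% drop-out, about 20 of 60 subjects on BELKYRA. Assumed, because the documents do not give them: normal changes, the baseline-to-final correlation ρ, and the BELKYRA share among evaluable subjects.

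**3. The plan's own figure.** Standardised effect 12/20 = 0.6; noncentrality 0.6 × √48 = 4.157. The exact noncentral-t power at n = 48 is 98.3%, not the stated 90%, and 32 subjects suffice for 90%. The drop-out step does reproduce: 48/(1 − 0.20) = 60. The power mismatch is a separate matter. Here 48 is used only as the planned evaluable number.

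**4. Benchmark: signed-rank on changes.** Simulation (10,000 trials per setting, n = 48, SD of change 20) gives power of 97.4% to 97.7% at mean change 12. At mean change 0 it rejects about 4.5% to 5.2% of the time.

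**5. Literal reading A: rank-sum test of changes by BELKYRA status.** Assumed split: 48 × 20/60 = 16 on BELKYRA, 48 − 16 = 32 without. With a true change of 12 in both groups, the test rejects in about 5% of trials (4.7% to 5.2% across runs). That is its null rate, because the groups do not differ. It says nothing about whether subjects improved.

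**6. Literal reading B: rank-sum test of final against baseline scores as independent samples.** To keep the SD of change at 20, the SD of a single score is 20/√(2(1 − ρ)). Ignoring the pairing overstates the standard error of a mean difference by 1/√(1 − ρ), and the rank test loses in a similar way.

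| ρ (assumed) | Score SD | SE overstated by | Power at mean change 12 | Rejection at mean change 0 |
|---|---|---|---|---|
| 0.3 | 20/√1.4 = 16.9 | 1.20 | 95% | 2.0–2.1% |
| 0.5 | 20/√1.0 = 20.0 | 1.41 | 88–89% | 0.7–0.8% |
| 0.7 | 20/√0.6 = 25.8 | 1.83 | 66–67% | 0.1% |

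Ranges show the spread between separate simulation runs.

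**7. The trigger.** Suppose the rule is to switch when absolute sample skewness exceeds c. With truly normal changes and n = 48, it switches in 76%, 54%, 14% and 0.6% of trials for c = 0.1, 0.2, 0.5 and 1.0. The unquantified wording therefore leaves open how often the fallback would be used at all.

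**The case against.** The best defence is that the SAP, read as a whole, means signed-rank. The same paragraph names it first, the output table allows no other nonparametric p-value, the protocol agrees twice, and a rank-sum test cannot run on one ungrouped column. Reading B is also conservative, so its cost is lost power rather than false claims of benefit. All of this stands, and it makes a drafting slip the likely explanation. It does not remove the contradiction: the conflicting sentence comes last, is attached to the only stated definition of non-normality, and cannot be checked against the redacted software section.

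The clash with SAP 10.2 is conditional. It arises only if the grouping were BELKYRA or gender, which the SAP never says; a grouping by visit would not breach that section.

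A reader might also infer that the switch to signed-rank is itself unsound and must go, because the hypothesis (Protocol section 2, SAP section 4) concerns mean change. With a true mean change of 0 and assumed gamma-type skewness of 0.5, 1 and 2, signed-rank rejects 6.0%, 9.0% and 21.6% of the time. The documents do not support making this a required change. They give no distribution for the changes. Under right skew nearly all of those rejections point to worsening: false improvement is about 1.1%, 0.5% and 0.1%, below the nominal 2.5%. Only left skew inflates false improvement (4.9%, 8.3% and 21.5%). Signed-rank is also the fallback that Protocol 11.4.1 prespecifies, so these figures do not measure the defect in the SAP sentence.

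**Conclusion.** The point holds as an inconsistency in the rule for the primary test and should be fixed. The one-way sentence conflicts with Protocol 11.4.1, the protocol synopsis, the SAP's own p-value row and SAP section 18. Confidence is high that the conflict exists; what the author meant is not known.

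The effect depends on two conditions: the fallback is triggered, and the sentence is taken literally. The p-value would then either answer a different question (reading A, about 5% rejection despite a real change of 12) or lose power as the assumed correlation rises (reading B, from about 95% down to about 67%, against about 98% for signed-rank). Both readings are hypothetical because no grouping is named.

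A reader might infer that the primary result will be wrong. The documents do not support that: if signed-rank is run, as the other passages indicate, the primary conclusion is unlikely to change at the planned effect. Nor do they settle whether PAAQ is affected, since SAP 10.3.2 and 10.3.2.2 point in opposite directions.

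**What to change.** **Required.** In SAP section 10, delete the one-way sentence. Name the Wilcoxon signed-rank test on within-subject changes as the only nonparametric replacement, for the primary endpoint and the five secondary FACE-Q scales covered by SAP 10.3. Reconcile SAP 10.3.2 with 10.3.2.2 on whether transformed PAAQ scores are tested; if they are, apply the same correction there.

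**Minor.** Replace the unquantified skewness wording with one numeric criterion, fixed before database lock.

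**Cost.** A short SAP amendment under Protocol 11.7 and no new data. Because the correction restores the protocol's own test, SAP section 18 needs no entry for it.

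**Optional, and a matter of preference.** Keep the paired t-test as primary throughout and report signed-rank as a sensitivity analysis. This departs from Protocol 11.4.1, so it would have to be recorded in SAP section 18. It also gives up some power if changes are left-skewed (at mean change 12 and assumed skewness −2, 94.2% for the t-test against 99.1% for signed-rank).
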